**Laboratory Testing :** Once the specimen is collected, study staff will follow instructions for sample preparation and testing. Luminex assays enable fast and accurate cytokine measurements by utilizing specially prepared microspheres, internally dyed with a graded mixture of red or infrared fluorescent dyes. Varying the degree to which the beads are internally dyed creates hundreds of different fluorescent profiles that can be individually interrogated and classified in a single sample. The BHP lab in Gaborone can conduct cytokine analysis using an ELISA quantitative; however, this assay is currently limited to only IL-6, ICAM1, and VCAM. Further, the ELISA is a single assay and sample processing would be costly and time-consuming compared to the Luminex multiplex assay.

**Specific Aim 4:** To determine the acceptability, feasibility, and costs of implementing point-of-care (PoC) syphilis testing and treatment among pregnant women in Botswana by offering: 1) dual HIV and syphilis PoC testing for pregnant women who are HIV uninfected/undiagnosed and 2) PoC syphilis testing for pregnant women with a known HIV infection with same-day treatment to women in the designated PoC clinic. PoC testing will be offered in addition to routine syphilis and HIV testing.

**Methods and Procedures:** An additional 200 antenatal patients at the designated PoC clinic and 200 at the ‘standard of care’ clinic will be enrolled (400 total). In the PoC clinics, participants who are HIV uninfected/ undiagnosed will be offered PoC dual HIV/syphilis testing and women living with HIV will be offered a PoC syphilis test. PoC participants will receive same-day results and treatment. Participants in the standard of care clinic will continue to receive the usual care.

Additionally, analysis will incorporate the data from 200 participants previously enrolled in the CT/NG parent study. These data will be used as a “pre-test” and will include all 100 women enrolled in the standard of care clinic and all 100 women enrolled in the PoC testing clinic.

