**Reporting and Treatment:** PoC Results: All participants will receive results in person, on the same day as testing. Treatment: Appropriate clinical staff will provide treatment per the Botswana MoH STI treatment protocols (see Treatment section below). Test results will be recorded in the participant obstetric record, clinic records, as well as into the study data form. Partner Services will be offered in the same manner as Aim 1; however, expedited partner treatment will not be an option for syphilis treatment. Standard of Care: Participants will continue to receive syphilis testing per Botswana national guidelines, which includes a VDRL/RPR test at the first ANC visit with delayed results and treatment. Typically, blood specimens are sent to a central lab for processing and results are provided to clinic staff after at least three days. Women are called to return to the clinic for receipt of results. Test results and treatment are recorded in the patient-held and clinic records.

**Data collection:** For participants in the PoC clinic, acceptability of PoC syphilis testing and receipt of treatment (with dates) will be recorded by study staff in study documents, and the patient-held and clinic records. Participants who decline and reasons for decline will be recorded in study records. For participants in the standard of care clinic, the patient-held and clinic obstetric records will be reviewed to identify receipt and dates of syphilis testing and treatment. We will also abstract obstetric and health information (para, gravida, gestational age, HIV status, antiretroviral treatment) from the records of all participants. At the time of enrollment, participants will be asked to respond to a short interviewer-administered questionnaire to collect basic sociodemographic information and costs incurred related to syphilis testing. Participants will also respond to another short survey on costs during their third trimester, which will be conducted over the phone. Cost-related questions will inquire about travel, overnight lodging, out-of-pocket care costs; and the opportunity costs associated with travel, wait, and appointment times. Participants testing positive will be eligible to participate in a brief semi-structured interview on partner notification and treatment.

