**Outcomes:** Our primary outcome is acceptability of syphilis testing at the first ANC visit (proportion tested for syphilis out of all eligible women receiving care in the study clinics during implementation of the study). For participants in the PoC clinic, acceptability will be defined as having a PoC test with recorded results. Those who decline PoC testing will be identified as not accepting and will be included in the denominator. For those in the standard of care, the numerator will be women who receive an RPR/VDRL syphilis test recorded in patient-held or clinic records. The denominator for both groups will be all women attending the study clinic during implementation and eligible for participation (1. Age  $\geq$  15 years, 2. Currently pregnant, 3. Attending first ANC visit, 4. 27 weeks of gestation or less, 5. Will reside

Title: The diagnosis and treatment of *Chlamydia trachomatis* and *Neisseria gonorrhoeae* in pregnant women to prevent adverse neonatal consequences.”

in Gaborone through the time of delivery and 1st postnatal visit, And 6. Mentally competent to understand the informed consent).

Additional outcomes will be related to treatment and costs. We will report the proportion of women who received treatment among those with a reactive syphilis test result. We will assess differences in any treatment, treatment completion, and time to treatment.

The primary cost outcome is the average unit cost per woman tested for each strategy and will include both patient-related costs and healthcare system costs. Healthcare-related cost data will be collected from in-country data sources. Patient data will be collected from the short survey.

**Analysis:** First, comparisons will be made across four groups of participant data: **1)** participants in the standard of care clinic enrolled as part of the CT/NG study prior to implementation of the syphilis testing sub-study called “Standard of Care pretest” (n=100); **2)** participants in the standard of care clinic enrolled as part of the syphilis testing sub-study called “Standard of Care post-test” (n=200); **3)** participants in the PoC clinic enrolled as part of the CT/NG study prior to implementation of the syphilis testing sub-study called “PoC pretest” (n=100); and **4)** participants in the PoC clinic enrolled as part of the syphilis testing sub-study called “PoC post-test” (n=200).

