To assess differences in receipt of syphilis testing, we will use a difference-in-difference (DiD) strategy, which takes the difference between two before and after differences (pre-post-test with comparison).[25] DiD will be performed using a logistic regression model with a variable for whether the individual was in the PoC clinic (PoC), whether or not it is the post period (Post), an interaction variable for the product of those two variables, and covariates. The primary outcome (Y) is the proportion of eligible women who are tested for syphilis at their first ANC visit:

$Y=a+bPoCPoC+bPostPost+bint(Post*PoC)+bcovariates$  Models will also be stratified by HIV status to see if PoC had a differential impact among WLH. Variables for which there were significant differences between the intervention and comparison group will be included in multivariable model.

Secondarily, will also assess receipt of treatment using DiD analysis by comparing the pre-test and post-test differences in terms of the proportions of participants who had a reactive test who: 1) received the first dose of treatment, and 2) completed treatment. Prevalence of syphilis will also be reported according to treatment group and HIV status as the proportion of individuals testing positive divided by the number of individuals tested. Exact binomial 95% confidence intervals for prevalence will be estimated. All analyses will be conducted with Stata 17.0 (Stata Corporation, College Station, TX).

To compare differences in costs, recurrent costs will be calculated per test, and capital and training costs will be summed and divided by the number of women tested. Those costs will be added to get an average unit cost for each strategy. For the intervention strategy, we will also calculate the average cost by HIV status at first ANC (i.e. the cost of delivering the dual HIV/syphilis test and the rapid syphilis). We will compare the mean costs using the non-parametric Mann-Whitney U test. For hypothesis 4, patient costs will be summed and an average patient cost will be calculated for each strategy, which will be compared using either the Mann-Whitney U test or Student's t-test. Cost components will be examined to determine key cost drivers and to identify potential efficiencies that could be achieved in future scale-up.

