**21. Study Timeline**

Table 1: Study Timeline	Start	Finish	Duration
Component and Task Name			
I. Preparation and Piloting	Jan 2020	Dec 2020	12 mo.
II. Enrollment and Follow-up (CT/NG)	Feb 2021	Mar 2022	11 mo.
III. Enrollment (syphilis post-test group)	August 2022	Feb 2023	7 mo.
IV. Follow-up only (CT/NG)	Apr 2022	Dec 2022	9 mo.
V. Data Analysis and Dissemination	Jan 2023	May 2023	5 mo.

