To estimate the budget impact of CT/NG testing among asymptomatic pregnant women, we will combine the total recurrent costs with capital, training, and start-up costs. Next, we will build a decision analytic model to estimate the cost per pregnant woman tested, tested positive, treated, and cured by time of delivery. If the intervention is effective, we will calculate the incremental costs per adverse neonatal outcome averted (e.g. neonatal CT/NG infections, preterm birth, and low birth weight) comparing the testing intervention with syndromic management. We will also estimate a cost-effectiveness ratio (ICER, difference in costs divided by difference in health outcomes), representing the change in costs per averted DALYs associated with preterm birth/low birth weight infants.

We will also perform a probabilistic uncertainty analysis where parameters are randomly sampled from probabilistic distributions to generate 10,000 parameter sets. For each parameter set, the model will run and produce a distribution of outcomes. We will provide the means and 95% confidence intervals for all cost and health outcomes. If the intervention is effective, we will also calculate mean incremental cost-effectiveness ratios (ICER; \$/ DALY averted) compared to syndromic management, assessing cost-effectiveness under a willingness-to-pay threshold informed by the WHO's Gross Domestic Product / capita threshold, which was US\$7,961 in Botswana 2019. We will also calculate the probability that the scenarios are cost-effective by assessing the proportion of ICERs that fall below the willingness to pay threshold.(3)

Sensitivity analyses will be conducted through one-way and multi-way methods to identify key cost drivers and assess how changing parameters impacts the overall costs and per patient cost of each strategy.(4)

Sample size

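### Aim 4 divides summed capital and training costs by the women tested, without annualising them or allocating shared laboratory capital, so that component of the unit cost is overstated and varies with enrolment

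*Protocol*

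**What the plan says.** The cost method for Aim 4 is in Protocol section 3 (Study Design), Specific Aim 4, Analysis. Recurrent costs are worked out per test. For one-off items, "capital and training costs will be summed and divided by the number of women tested". Then: "Those costs will be added to get an average unit cost for each strategy". The Outcomes paragraph of the same aim makes this the main cost endpoint: "The primary cost outcome is the average unit cost per woman tested for each strategy and will include both patient-related costs and healthcare system costs".

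The other relevant facts are spread across the protocol:

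- Aim 4, Methods and Procedures: 200 women are to be enrolled at the point-of-care (PoC) clinic and 200 at the standard-of-care clinic.
- Section 21 (Study Timeline): enrolment of this group runs from August 2022 to February 2023, given as 7 months.
- Aim 4, Reporting and Treatment: under standard care, "blood specimens are sent to a central lab for processing".
- Aim 4, Laboratory Testing: women in the PoC clinic also receive the routine RPR/VDRL test.

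Neither document mentions annualisation, depreciation, useful life, a discount rate for capital, or how shared capital is to be allocated.

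**The concern.** Equipment and training normally serve beyond the study that pays for them. If the whole outlay is divided by the women tested in one short study, the result measures study size as well as technology: halving enrolment doubles this component although nothing about the test has changed. That matters because the figure enters the primary cost outcome, and because the protocol wants the cost components to inform future scale-up, where cost at real service volume is the relevant quantity.

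The comparison between strategies has a related gap. Standard-care testing relies on a central laboratory, and the plan does not say how much of that laboratory's capital is charged to the study women. Charging it all to about 200 women would inflate the standard-care figure. Leaving it out as already paid for would favour standard care. Because PoC-clinic women have the laboratory test too, it is also unstated whether laboratory capital enters one strategy or both.

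**Working it through.** **No plan figure to reproduce.** The documents give no prices, lives, discount rate or unit cost. The one relevant number, 7 months, checks: August 2022 to February 2023 inclusive is 7 months.

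**Inputs from the protocol.** At most 200 women tested per strategy; a period of T = 7/12 year.

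**Assumed inputs.** Useful life L of 1 to 10 years; discount rate r of 3% or 5%; a range of values for s, the capital and training share of the unit cost as charged. The same 200 women are taken as the throughput over the 7 months.

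**Step 1: overstatement of the capital and training component.** The annuity factor is A = (1 - (1 + r)^-L) / r. The annualised charge for the period is outlay × T / A, so full outlay overstates it by f = A / T.

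| Life (years) | A at 3% | f at 3% | A at 5% | f at 5% |
|---|---|---|---|---|
| 1 | 0.971 | 1.66 | 0.952 | 1.63 |
| 2 | 1.913 | 3.28 | 1.859 | 3.19 |
| 3 | 2.829 | 4.85 | 2.723 | 4.67 |
| 5 | 4.580 | 7.85 | 4.329 | 7.42 |
| 10 | 8.530 | 14.62 | 7.722 | 13.24 |

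Without discounting, A = L and f runs from 1.71 (1 year) to 17.14 (10 years).

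For illustration, take an outlay of 1,000 currency units:

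- As written: 1,000 / 200 = 5.00 per woman.
- Annualised over 5 years at 3%: (1,000 / 4.580) × (7/12) / 200 = 0.64 per woman.
- As written, with 100 women tested instead of 200: 1,000 / 100 = 10.00 per woman.

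**Step 2: effect on the whole unit cost.** The unit cost also holds recurrent and patient costs, which annualising does not touch. The ratio of the unit cost as charged to the annualised one is 1 / ((1 - s) + s / f). With f = 7.85 (5 years, 3%):

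- s = 10%: 1 / (0.90 + 0.0127) = 1.10
- s = 25%: 1 / (0.75 + 0.0318) = 1.28
- s = 50%: 1 / (0.50 + 0.0637) = 1.77

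**Step 3: share needed for a threefold overstatement of the whole unit cost.** s = (1 - 1/3) / (1 - 1/f). At 3% this is 76% for a 5-year life, 84% for 3 years and 72% for 10 years. At a 1-year life it cannot happen, because f is below 3.

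**The case against.** The strongest reply is that the plan is silent rather than wrong. It does not say that the summed capital costs are purchase prices, that the women tested are study participants only, or that the 7-month enrolment window is the costing period. Health-system costs come from in-country sources, which could supply annualised values. This is possible, but nothing in the text points to it. The formula is stated as complete (sum, divide, add), and an analyst who meant to annualise would still lack a life, a rate and a throughput.

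The second reply concerns size, and most of it stands. A reader might infer from the component multiples that unit costs as a whole are inflated several-fold. The documents do not support that: they give no capital share, and a threefold effect would need a share of roughly three-quarters. The capital share may be small on the PoC side, because the dual test is an immunochromatographic rapid test and no instrument is listed for it. For training, a short life is arguable, and at 1 year the multiple is only about 1.6-1.7.

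Third, a reader might infer that the method penalises the PoC strategy. That cannot be derived either. Laboratory capital could be charged in full, omitted, or counted in both clinics, in which case it might cancel.

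Fourth, it is tempting to extend the point to the SAP, where "we will combine the total recurrent costs with capital, training, and start-up costs". That sentence serves a budget-impact estimate, for which full outlay is appropriate. The decision model that follows is a separate step for chlamydia and gonorrhoea testing. Aim 4 plans no cost-effectiveness ratio, and its unit cost is not stated to feed the SAP's ratios. The SAP's sensitivity analyses belong to that evaluation and do not cover Aim 4.

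Finally, acceptability is the primary outcome of Aim 4, and cost as implemented, start-up included, is a legitimate descriptive result. The planned review of cost components would help to show how large the one-off items are, but it would not correct the unit cost.

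**Conclusion.** The point holds for the capital and training component of the Aim 4 unit cost. Followed as written, the formula loads one-off costs on at most about 200 women per strategy and makes the component depend on enrolment. Under the assumed lives and a 3-5% rate, the component is overstated about 1.6-1.7 times (1 year), 4.7-4.9 times (3 years), 7.4-7.9 times (5 years) or 13-15 times (10 years). These multiples rest on the plain reading of the formula and on taking 7 months as the period served.

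The effect on the whole unit cost is not known, because the capital share is not given; it is about 1.1 to 1.3 times if that share is 10-25%, with a 5-year life at 3%. The missing allocation rule for laboratory capital leaves the comparison between strategies open to bias of unknown direction and size.

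**What to change.** In the Analysis text of Aim 4 (Protocol section 3), replace the division with this rule, identical for both strategies:

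1. Convert capital and training costs to an equivalent annual cost, with a stated useful life for each item and a stated discount rate.
2. Charge only the share used for syphilis testing.
3. Divide by the actual annual throughput of the facility where the item is used, the central laboratory included, counting non-study use.
4. Count the RPR/VDRL test that PoC-clinic women also receive.
5. Report the unit cost with and without one-off start-up costs.
6. Vary useful life and throughput in a sensitivity analysis.

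The SAP's budget-impact sentence needs no change.

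The cost is protocol wording and a spreadsheet change, with no new patient data. The downside is that useful life and throughput become stated assumptions, which the sensitivity analysis then has to carry.

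### Aim 4 plans to compare mean costs with a Mann-Whitney U test, which does not test means and tells nothing about a unit cost that is one figure per strategy

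*Protocol*

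**What the plan says.** All of this is in Protocol section 3, Specific Aim 4.

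- **Target (Outcomes).** "The primary cost outcome is the average unit cost per woman tested for each strategy and will include both patient-related costs and healthcare system costs". On sources: "Healthcare-related cost data will be collected from in-country data sources"; patient costs come from a short survey of each woman.
- **How the unit cost is built (Analysis).** Recurrent cost is worked out per test; "capital and training costs will be summed and divided by the number of women tested". Then: "Those costs will be added to get an average unit cost for each strategy". There is one further split: "For the intervention strategy, we will also calculate the average cost by HIV status at first ANC".
- **Test for that comparison.** "We will compare the mean costs using the non-parametric Mann-Whitney U test".
- **Test for patient costs.** These are averaged by strategy, "which will be compared using either the Mann-Whitney U test or Student's t-test". No rule for choosing is given.

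No confidence interval, bootstrap or regression for mean cost is planned for Aim 4. The SAP's probabilistic uncertainty analysis, which does report means and intervals, concerns the CT/NG test-and-treat intervention and not the syphilis costs.

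**The concern.** The target and the test do not match. A Mann-Whitney U test asks whether a woman drawn from one group tends to have a higher value than a woman drawn from the other. It answers a question about means only if the two distributions have the same shape. Costs are a poor setting for that condition, because a few expensive women can carry much of the mean while hardly moving the ranks.

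There are two separate difficulties. The health-system part has no described variation between women, so there is nothing for a rank test to work on. The patient part does vary between women, but two tests of different hypotheses are left open. Results are to go to the Ministry of Health (section 22), and a p-value from this plan would be read as evidence about mean cost, which it is not.

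**Working it through.** The documents give no cost data, alpha, SD, expected difference or power for the Aim 4 cost comparison, so there is no stated figure to reproduce. From the protocol I take 200 women per post-test group. I assume a two-sided 0.05 level and the cost distributions stated below, in arbitrary units.

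**1. The health-system unit cost.** As built, unit cost = recurrent cost per test + (capital + training) / women tested. That is one number per strategy.

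- One value against one: exact p = 1.0. The test cannot reject.
- Two values against one, using the HIV-status split within the intervention: the most extreme ordering gives p = 0.67. The test still cannot reject.
- Constant copied to 200 women per group: U = 0, against an expected 200 × 200 / 2 = 20,000. With ties, the variance is (200 × 200 / 12) × [401 − 2(200³ − 200) / (400 × 399)] = 3,333.3 × (401 − 100.25) ≈ 1,002,500, so SD ≈ 1,001. With continuity correction, z = 19,999.5 / 1,001 ≈ 20 and p ≈ 9e-89. The result is identical for 10.00 v 10.01 and for 10 v 100.

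The p-value therefore depends on how the data are laid out, not on the cost difference. This step needs no distributional assumption.

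**2. Patient costs.** Simulated trials used 200 per group and gamma costs, with the gamma shape varied from 0.5 to 8 because nothing in the documents fixes it. With 1,000 replicates the simulation standard error is at most √(0.25/1,000) ≈ 1.6 points.

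| Assumed costs | True means (PoC v standard of care) | Mann-Whitney result |
|---|---|---|
| Standard of care: 90% at mean 20, 10% at mean 200. PoC: no tail | 38 v 0.9×20 + 0.1×200 = 38 | rejects in 65-100% |
| Same standard of care; PoC cheaper | 30 v 38 | calls PoC dearer in about 20-100% |
| Standard of care: 95% at mean 30, 5% at mean 150. PoC: no tail | 36 v 0.95×30 + 0.05×150 = 36 | rejects in 9-97% |
| Same distribution in both arms | equal | rejects in about 5% |

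The shape matters a great deal. In the milder-tail row, rejection is 9% at shape 0.5, 16% at shape 1, 65-69% at shape 4 and 97% at the top of the range. At shape 4 in the first row, Welch's t-test rejects in about 7%. In the second row it calls PoC dearer in well under 1% of trials.

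**3. Missing a saving.** Let everyday cost be 20 in both arms, with 5% of standard-of-care women at 200. The means are then 20 v 0.95×20 + 0.05×200 = 29. At shapes 2 and 4, Mann-Whitney detects the saving in about 13-15% of trials and Welch's test in roughly 76-88%.

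**4. Same-shape check.** With lognormal costs (sigma 0.8 in both groups), Mann-Whitney rejects in 4.3% at equal means and never calls PoC dearer when it is 10% cheaper. The fault appears only when the shapes differ.

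**The case against.** **The one-sided tail is an assumption, and the documents only partly support it.** PoC women also have the routine RPR/VDRL, so some may be recalled. Women treated in either arm make return visits. The protocol puts syphilis prevalence below 5%, so a 10% tail is generous. If recall for results applies to all standard-of-care women, it raises everyone's cost and is not a tail. With the same 5% tail in both arms, rejection is 5-6%. This stands: a reader might infer from the simulations that the planned test will point to the wrong strategy, and the documents do not support that. They support only that it can. Different shapes remain plausible, since recall for results belongs to standard of care and travel and lodging are costed, but the size is unknown.

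**A rank test of the unit cost is not bound to be significant.** A reader might infer that it is. That follows only if the constant is copied to every woman, which the protocol never says. Taken literally, one value per strategy gives p = 1.0. The Outcomes text also brings patient costs into the primary cost outcome, so a per-woman total could be formed, though the Analysis text does not describe one. The fair statement is that the unit of analysis is unclear and that neither layout gives an informative test. In a per-woman total the rank test would still not test the mean.

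**Part of the remedy is already there.** Average costs are to be calculated for each strategy, so the mean difference will be visible, and a t-test is permitted for patient costs. What is missing is an interval for the difference and a rule for choosing the test.

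**Conclusion.** The point holds. The sentence on mean costs names a test that does not test means, and for the health-system unit cost the result is uninformative in either layout (p = 1.0, or about 9e-89 regardless of the difference). Both conclusions rest on the protocol's own wording. For patient costs the choice of test is open, and the choice can change the conclusion when the distributions differ in shape. The sizes, 65-100% and 9-97% rejection at equal means against about 5% for identical distributions, rest wholly on assumed gamma costs and are illustrations, not forecasts.

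A reader might take this as a fault that must be cured before the trial can be interpreted. The documents do not support that. Aim 4's primary outcome is acceptability of testing, costs are among its additional outcomes, and neither the sample size nor the mother-to-child transmission endpoint depends on this test. It should be fixed before the cost analysis is run.

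**What to change.** Replace Mann-Whitney as the comparison of mean costs in the Aim 4 Analysis text:

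- **Patient costs:** pre-specify the difference in arithmetic means (PoC minus standard of care) with a bootstrap 95% CI, and Welch's t-test as a check. Remove the open choice between two tests.
- **Health-system unit cost:** report one figure per strategy, and by HIV status within the intervention, without a hypothesis test. Vary its inputs in sensitivity analysis.
- **Total cost:** form the difference as the patient-cost difference plus the deterministic unit-cost difference. The bootstrap interval then shifts by that constant. State that it reflects variation in patient costs only, with unit-cost uncertainty shown by the sensitivity analysis.
- **Unit of analysis:** say for each comparison whether the data are per woman or per strategy.

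The cost is protocol wording and a few lines of code. No new data are needed.
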